#### *Providers: Site Visits*

Ahead of site visits, the research team will provide an email template (Appendix 11) for SE managers to send to SE staff prior to site visits. These emails will inform staff that research personnel will be on site to observe unit operations related to implementation and to conduct interviews with available staff involved in the implementation process.

#### *Providers: Key Informant Interviews*

Ahead of site visits, the research team will provide an email template (Appendix 11) for SE managers to send to SE staff prior to site visits. These emails will inform staff that research personnel will be on site to observe unit operations related to implementation and to conduct interviews with available staff involved in the implementation process. A study information sheet regarding the interviews will be included for staff to review prior to the visit to ask any questions.

### *Staff Persons Delivering Study Interventions*

The research team will provide information in person, or by phone/secure video conference to VRC staff persons who will be delivering study interventions and taking part in training, consultation, and audit and feedback processes involving monthly fidelity data collection. As noted, participation as intervention facilitators will be discussed with SE managers and potential interested staff, including all relevant implementation activities and expectations (facilitation of weekly groups, etc.).

### **5.3.4 Payments to Subjects**

#### *Veterans*

Participants in both study arms will receive \$20 for each completed outcome assessment (baseline, 12-week, 6 & 9 month only). After obtaining informed consent, the onsite RA will administer a baseline assessment to gather assessment data (see Sections D8a-c, Section E3d). Each assessment will take approximately 60 minutes. Participants will not be compensated for attendance in weekly group sessions (CBTw or psychoeducation, respectively). Participants will not be compensated for transportation costs.

#### *Providers*

In accordance with VA policy, VA staff will not receive payment for study participation.

### **5.4 Informed Consent Procedures**

#### **Veterans**

We are requesting a waiver of informed consent for recruitment. Prior to recruitment, we will obtain Central IRB and Local VA R&D Committee approval at sites to conduct this proposed research. At each site, we will consult with SE staff and gain permission to recruit their patients (Veterans on their caseload who have SMI and are unemployed, those who they deem appropriate for the study). Next, SE staff will inform potential Veteran participants of the study. If those Veterans express interest, the SE staff person will provide or read the Veteran a study flyer.

Next, an onsite research assistant will use the electronic medical record to screen for inclusion criteria (SMI diagnosis and age 18 or older) of potential participants who have expressed interest in the study. If Veterans meet the SMI diagnosis and age inclusion criteria, the research assistant will then call these Veterans and screen for the other inclusion and exclusion criteria (confirm unemployed status, goal of competitive work, and no prior participation in a intervention CBT tailored for work). If all criteria are met, the RA will ask if the Veteran would like to participate in the study. Participants who confirm that they would like to participate in the study will be scheduled for a pre-randomization baseline assessment with the onsite (blinded) research assistant. At the start of the assessment, verbal informed consent will be obtained prior to further study involvement.

RA's, blinded to which group the participant is randomized to, will obtain verbal informed consent. All study group sessions will be audio recorded; all audio recordings will explicitly

capture the participants consent to be audio recorded. Audio recordings will be transcribed by research study personnel and deidentified. All individuals obtaining informed consent (RA's at local sites) and LSI's will be trained by the PI, [name], on appropriate informed consent procedures. Travel funds have been designated for [name] and other RLR personnel to travel to the local sites in order to provide training in informed consent procedures, as well as other study procedures. As deemed necessary, these trainings will be conducted virtually to minimize non-essential in-person interaction. At regularly scheduled team conference calls, the PI or Project Manager will periodically review informed consent procedures and address any questions or concerns. Moreover, all individuals obtaining informed consent and LSI's will have completed CITI Human Subjects Trainings for VA Human Subjects Research.

### ***Providers***

For all staff participating in the study, we will obtain any necessary approvals for their participation from service unions.

### ***Staff Persons Delivering Study Interventions***

As described above, in consultation with SE managers at each site, vocational rehabilitation counselors with interest in CBTw and psychoeducation will be chosen as intervention facilitators (up to 4 staff persons per study condition at each site). Separate staff persons will facilitate CBTw and psychoeducation interventions at each site. During the initial site visit, research personnel will discuss the role of intervention facilitators. Once consent is provided by staff, the initial training and intervention implementation will begin. All study group sessions will be audio recorded; all audio recordings will explicitly capture the participants consent to be audio recorded. Audio recordings will be transcribed by research study personnel and be deidentified.

### ***Key Informant Interviews***

Key informants who will take part in interviews (occurring at pre-implementation, early implementation, mid implementation, and late implementation) include staff delivering CBTw intervention, SE program managers, and other SE staff persons involved in CBTw implementation. Ahead of site visits, study personnel will email study information sheets (using VA encrypted email). The SIS will be further reviewed onsite (for onsite interviews) or over the phone (if interviews occur over the phone) with potential participants. Consent will be implied by participant/staff's participation in the interview. All interview will be audio recorded; all audio recordings will explicitly capture the participants consent to be audio recorded. Audio recordings will be transcribed by research study personnel and be deidentified.

## **5.5 Inclusion/Exclusion Criteria**

### **5.5.1 Veterans**

#### ***Inclusion criteria***

1) Unemployment, defined as no current participation in a competitive job; 2) a competitive work goal; 3) Presence of a serious mental illness (required to receive SE services); 4) Receiving SE services; 5) Age 18 or older.

#### ***Exclusion criteria***

1) Previous participation in CBT geared toward work; 2) Presence of a severe medical or cognitive impairment that will prevent participation in the study.

#### *Details on Veteran inclusion criteria*

Employment Status: Unemployment is defined as a lack of a competitive job at baseline. Veterans meeting inclusion criteria who hold noncompetitive jobs (e.g., transitional work experiences) are not considered competitively employed and will be eligible to participate in the study.

Competitive work denotes a job that it is open and available to everyone, not reserved exclusively for persons with disabilities; competitive jobs pay minimum wage or above. Casual labor, such as odd jobs, does not constitute competitive work. Our prior research suggests that unemployed Veterans in SE often have competitive work goals that include finding a good job, maintaining a job over time, and increasing work hours and wages.

Enrollment in SE services: Participants must be formally enrolled in SE services at the sites described in Section D2, "Study Sites". Information regarding nature of these services is described in Section D5.

Diagnosis of serious mental illness & work impairment: To be eligible for the study, participants must have a lifetime diagnosis of a SMI including: affective disorders including major depression and bipolar disorders; schizophrenia spectrum disorders including schizophrenia and schizoaffective disorder; and PTSD. In accordance with the standard definition of SMI, no other diagnoses will be included. As noted, all participants will have a documented work impairment & SMI diagnosis in order to qualify for SE services at the three sites. SMI diagnosis will be further verified during the eligibility screening process.

#### *Including Veterans with SMI*

The inclusion of Veterans with SMI was chosen for 3 reasons: 1). These represent the average Veterans served nationally in VHA SE services; restricting to a narrow diagnostic group would not produce a generalizable understanding of the outcomes of CBTw in regular care. 2) CBTw was designed for Veterans with SMI across the diagnoses that are included in WORKWELL. CBTw pilot findings demonstrate that these diagnostic groups did not significantly differ on outcomes at the follow-ups. Further, the developmental CBTw pilot found that the inclusion of Veterans with various SMI diagnoses was not a barrier; participants reported that the experience of vocational dysfunction was unifying. 3). Maladaptive cognitive and behavioral factors that influence work functioning are consistent across SMIs and are effectively addressed using CBT.

#### **5.5.2 Staff**

##### *Inclusion criteria:*

1) Key informants participating in interviews may be supported employment staff persons (frontline staff persons, SE manger, administrative staff, etc.) at a participating VA site. Staff persons delivering the interventions will be vocational rehabilitation counselors.

##### *Exclusion criteria:*

None

## 5.6 Study Evaluations

### Data Collection Protocol for Study Aims 1 & 2

Conducted by onsite research assistants (RAs) blinded to arm assignment, outcomes assessments will take place at four time points: baseline, 12-weeks (posttreatment), 6 months, and 9 months. In addition, work outcomes will be collected monthly on Work Update Forms to lessen the burden of Veteran recall. This schedule will elucidate the trajectory of treatment effects over time, including early response and more sustained impacts on outcomes. Participants will receive \$20 for each completed outcome assessment (baseline, 12-week, 6 & 9 month only). After obtaining informed consent, the onsite RA will administer a baseline assessment to gather assessment data. Each assessment will take approximately 60 minutes. All baseline assessments will take place in person; 12 week, 6 month, and 9 month assessments may be done in person (first consideration) or by phone.

The primary work outcome, total weeks worked in competitive jobs, will be collected monthly and analyzed at all assessment points with the primary endpoint being 6 months to allow adequate time for CBT skills to be practiced and solidified. The 12 month endpoint will examine whether there are sustained effects of CBTw and determine whether there are differences between the arms on achievement of steady competitive work (Aim 1). Health and recovery outcomes will be examined between the arms at all assessment points to understand the impact of CBTw; the relationship between weeks worked and these outcomes will also be examined at all assessment points (Aim 2). Work outcomes may be collected in person or by phone.

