### 3.2. Specific Aims & Hypotheses.

Aim 1. Test the effects of CBTw + SE compared to a time and format matched active control of psychoeducation + SE on competitive work outcomes across the 9 month study period. A total of 276 unemployed Veterans with SMI will be randomized to CBTw + SE or the control arm of psychoeducation + SE. Assessed at posttreatment (12 weeks), 6 months (primary endpoint), 9 months and 12 months (to examine sustained effects), the primary outcome will be total weeks worked in competitive jobs. A secondary work outcome, achievement of steady competitive work (i.e. working at least 50% of the follow-up), will be compared between study arms across the 12 month follow up.

Hypothesis 1: Compared to the control arm, participants in the CBTw + SE arm will work significantly more weeks and will be more likely to become steady workers.

Aim 2. Test the effects of CBTw + SE compared to the control arm of psychoeducation + SE on health and recovery at posttreatment (12 weeks), 6 month and 9 month follow up periods. The study will determine the effectiveness of CBTw to improve key health and recovery outcomes including health-related quality of life, suicidal ideation, subjective recovery, symptoms, and mental health service utilization.

Hypothesis 2a: Compared to controls, participants in the CBTw + SE arm will have greater improvement on subjective recovery and health-related quality of life, and decreases in mental health symptoms, suicidal ideation, and inpatient service utilization.

Hypothesis 2b: Greater participation in competitive work will predict improvements in these outcomes over time.

Aim 3. Guided by the RE-AIM implementation framework, conduct an implementation evaluation of CBTw to inform future wide scale roll-out of the intervention across the VHA. Existing Vocational Rehabilitation Counselors (VRCs) at the 3 VA SE programs will deliver CBTw, supported by an initial implementation strategy bundle—site tailored implementation planning, CBTw training, and weekly consultation including audit and feedback. Informed by the RE-AIM implementation framework, data will be collected and utilized to tailor implementation during the study, with assessment of the following RE-AIM domains:

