Aim 1: Work outcomes. The primary analysis is intention-to-treat and the primary outcome is total weeks worked in competitive jobs with primary endpoints of 6 and 9 months. Power estimate for total weeks worked was calculated using simulated data from a three-level linear regression model to account for the nested structure of the data. Simulation studies are the most flexible method for power analysis which can be tailored to any kinds of analyses. SAS 9.4 was used to generate 1000 datasets from each hypothesized model with plausible effect sizes for parameters of interest based on pilot data. Power estimates are based on the percentage of the datasets (replications) in which the parameters were significant. Based on the open trial pilot data, an ICC of .077 was estimated for the clustering effect of cohort and an ICC of .2 for repeated measures. Our pilot data show that CBTw significantly increased total weeks worked at 6 months ($f^2 = .15$). It is anticipated that there will be a larger increase in total weeks worked over time for the treatment arm. With the target sample size, there will be 97.6% power to detect even a small study arm by time interaction effect ($f^2 = .03$) with type I error set at .05. Further, the outcome distribution is likely to be non-normal. Although power will be attenuated by this non-normality, power to detect the target effects is still expected to be sufficient (>80%). For the binary outcome of achievement of steady competitive work, CBTw pilot data show that 49% of participants who were unemployed at baseline became steady workers at 6 months. In WORKWELL, it is expected that 5-10% more participants will acquire work and become steady workers during by the 9 month follow-up. Thus, power estimates may be conservative. In the control arm, it is anticipated that approximately 34% will become competitively employed and a lesser number will be steady workers by 9 months, based on VHA program evaluation data reporting 1-year SE outcomes. Based on the effect size, simulated data was used from two level logistic regression models, finding that the target sample size will provide > 99% power to detect the treatment effect, accounting for a conservative estimate of 13% attrition. If more participants gain competitive employed in the control arm (~50%), there will be >80% power to detect this effect.

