Hypothesis 1: For the outcome, total weeks worked in competitive jobs, three-level linear regression models will be used to test the effects of CBTw + SE compared to psychoeducation + SE over time, with predictors of study arm, arm by time interaction, site, and interaction between site and key predictors, covariates, as well as random effects to accommodate the potential non-independence due to repeated measures and group cohort effects. The time effects could be linear or nonlinear; these possibilities will be examined by treating time as continuous or categorical. If the outcomes are not normally distributed, robust maximum likelihood estimation method will be used to correct the standard error estimates for nonnormality. In the case of excess of zeros for this outcome, hurdle negative binomial models, a reliable method to analyze zero inflated longitudinal data of this nature, will be utilized. For the binary outcome, steady competitive work status across the 9-month study period, two-level logistic regression model will be used with the same set of predictors as in the linear models, with random effects to accommodate the potential non-independence due to group cohort effects.

Aim 2 Analyses: Health and Recovery Outcomes

To test **Hypothesis 2a**, Two-level linear regression models accounting for the nested nature of the data (repeated measures nested within individuals) will be used to examine the effects of CBTw + SE services compared to psychoeducation + SE on the change of each of the continuous outcomes including recovery (RAS), health-related quality of life (PCS & MCS), symptoms (DSM), and suicidality (SSI) over time (baseline and 3-, 6-, 9-months follow-ups). The scores of the outcome measures are calculated by averaging the corresponding items. The models are the same as those in Aim 1 analysis except that the outcomes are different. It is hypothesized that CBTw + SE will lead to a greater improvement on the health and recovery outcomes (indicated by a significant arm by time effect). If the outcomes are not normally distributed, robust maximum likelihood estimation method will be used to correct the standard error estimates for nonnormality.

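### Total weeks worked at 9 and 12 months is to show sustained effects, but with no counting window or post-6-month contrast defined, a gain made by 6 months can pass as a lasting one.

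*Protocol*

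**What the plan says.** Protocol 3.2 (Aim 1) lists the assessments as 12 weeks, 6 months as the primary endpoint, and then "9 months and 12 months (to examine sustained effects), the primary outcome will be total weeks worked in competitive jobs". Protocol 5.6 (Study Evaluations) says that "total weeks worked in competitive jobs, will be collected monthly and analyzed at all assessment points with the primary endpoint being 6 months", and of the last time point: "The 12 month endpoint will examine whether there are sustained effects of CBTw". The Methods part of the Protocol abstract also ties 9 months to sustained effects.

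The SAP's power section for Aim 1 gives the expected pattern: "It is anticipated that there will be a larger increase in total weeks worked over time for the treatment arm". It names "primary endpoints of 6 and 9 months". Its Aim 1 model has "predictors of study arm, arm by time interaction, site, and interaction between site and key predictors", and on the coding of time it says that "these possibilities will be examined by treating time as continuous or categorical".

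Three things are absent from both documents: a definition of the window over which weeks are counted at each visit, an outcome restricted to the time after month 6, and a contrast of 9 or 12 months with 6 months. The SAP has no analysis of work at 12 months and does not speak of sustained effects.

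**The concern.** Aim 1 asks two questions: whether CBTw raises weeks worked by 6 months, and whether the benefit lasts. One variable is to answer both. A total counted from baseline suits the first question. It suits the second poorly, because it cannot fall, and whatever separated the arms by month 6 is still in every later total.

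A reader of a significant 9- or 12-month difference would naturally conclude that Veterans in the CBTw arm were still working more at that time. The same result can arise when they worked more early and then exactly as much as controls. Durability matters here, because Protocol 3.3 says that the operational partners will implement CBTw broadly if effectiveness is shown.

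**Working it through.** **Carry-forward.** Let D be the arm difference in weeks worked from baseline to month 6, and suppose that the arms work equally afterwards.

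| Measure | 6 months | 9 months | 12 months |
|---|---|---|---|
| Running total from baseline | D | D + 0 = D | D + 0 + 0 = D |
| Weeks since month 6 | – | 0 | 0 |

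This needs no assumption beyond the running total.

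**The planned interaction.** Suppose that D builds up evenly over months 0–6 and that time is linear over visits at 3, 6, 9 and 12 months. The deviations from the mean time of 7.5 are −4.5, −1.5, 1.5 and 4.5, with sum of squares 45.

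- Running totals (D/2, D, D, D): slope = (−2.25 − 1.5 + 1.5 + 4.5)D/45 = +0.050D per month.
- Weeks per quarter (D/2, D/2, 0, 0): slope = (−2.25 − 0.75)D/45 = −0.067D per month.

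With running totals and linear time, the arm-by-time slope is positive although the effect has ended. With categorical time, the arm terms would show a flat difference from month 6, but only if someone chooses to contrast those visits.

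**How often the later total would be significant.** The plan gives no figure for this. Its nearest figure, 97.6% power for an interaction of f² = .03, comes from a simulation whose full settings are not stated. It can be neither confirmed nor refuted, and nothing below depends on it.

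Inputs from the documents: 276 × 0.87 = 240 analysed, so 120 per arm; type I error .05 (taken as two-sided); f² = .03 (the SAP's target, stated for the interaction but used here as a 6-month difference) and .15 (pilot, 6 months); cohort ICC .077; groups of up to 8.

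Assumptions: the correlation ρ between early and later weeks is .2 to .8; the SD of weeks in months 6–12 equals that of months 0–6; the SD for months 6–9 is 0.6 of it.

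- d = 2√f² = 0.346 or 0.775.
- Variance of the total relative to 6 months: 1 + 0.36 + 1.2ρ at 9 months; 2 + 2ρ at 12 months.
- Design effect: 1, or 1 + 7 × .077 = 1.539.
- z = d·√(60 / (relative variance × design effect)); probability ≈ Φ(z − 1.96).

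Example with f² = .03, ρ = .2 and no clustering, at 12 months: z = 0.346 × √(60/2.4) = 1.73, and Φ(−0.23) = 41%. With ρ = .8 and clustering: z = 0.346 × √(60/(3.6 × 1.539)) = 1.14, and Φ(−0.82) = 21%.

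| Effect that ended at 6 months | 9-month total significant | 12-month total significant | Weeks after month 6 |
|---|---|---|---|
| f² = .03 | 30–56% | 21–41% | 5% |
| f² = .15 | 89–99.7% | 72–97% | 5% |

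**A weekly model, and its limit.** Take 120 per arm, 34% of controls ever employed by one year (the SAP's figure) and an assumed 2% weekly job loss. Multiply the CBTw job-start rate by 2 to 3 up to week 26, then force both arms to the same employment rate. Differences of 2.0 to 3.7 weeks at week 26 remain 2.0 to 3.7 at weeks 39 and 52. Running totals favoured CBTw significantly in 37–82% of trials at 9 months and 22–58% at 12 months, against 2–3% for weeks 27–39 or 40–52.

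That forcing is artificial. At week 26 the model has 27% to 37% of the CBTw arm at work against 15% of controls, and the whole excess must vanish in one week. If only the job-start effect ends and early jobs are lost at 2% per week, weeks 27–39 favour CBTw in 52–94% of trials and weeks 40–52 in 28–66%.

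**The case against.** The strongest reply is that the running total is inferred. Neither document calls the variable cumulative. The missing-data sections refer to work by follow-up period, and the SAP's repeated-measures ICC of .2 fits counts per period better: running totals of three equal, uncorrelated intervals have average variance (1 + 2 + 3)/3 = 2 and average covariance (1 + 1 + 2)/3 = 1.33, a ratio of .67. This stands as evidence that the window is undefined. It does not remove the problem. The wording of the outcome and the expected growth over time point to a running total, and if weeks were counted since the previous visit, the 6-month value would no longer be the total up to the primary endpoint.

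A reader might go further and infer that the design cannot tell continued work from an early gain, or that no reading of the plan serves both questions. The documents do not support that. Work is recorded monthly, and a categorical arm-by-time model contains the needed contrast; it is simply not named.

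A reader might also take the simulated percentages as the trial's false-claim rate. They are not. They assume an abrupt loss of the whole employment advantage, the weekly model ignores cohort clustering, and at f² = .03 a significant 12-month total is the minority result.

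Finally, one may call a retained cumulative advantage a lasting benefit. That is a fair description of total work done, but a different statement from still working more.

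**Conclusion.** The point holds as a gap in the definition of the analysis. The Protocol uses total weeks worked at 9 and 12 months to examine sustained effects without defining the counting window or a post-6-month contrast. On the plain reading, the 6-month difference passes unchanged into the later totals, so a significant later total is not evidence of a sustained effect on its own. The carry-forward is exact, given a running total. Its frequency (21–41% at 12 months for f² = .03; 72–97% for f² = .15) is illustrative and rests on the assumed correlations and SDs and on an effect that stops completely at 6 months. The 6-month primary analysis is not touched. The sustained-effect purpose appears only in the Protocol, so the absence of a 12-month work analysis from the SAP has to be settled at the same time.

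**What to change.** 1. In Protocol 3.2 and 5.6 and in the SAP's Aim 1 analyses, state that the 6-month primary outcome is cumulative competitive weeks from baseline to 6 months.
2. Pre-specify the sustained-effect outcome as competitive weeks worked within months 6–9 and within months 9–12. The 6–9 contrast equals the change in the cumulative arm difference from month 6 to month 9; the 9–12 contrast is the further change to month 12.
3. Base any statement that effects are sustained on the arm contrast in those intervals, and report the 9- and 12-month cumulative totals descriptively.
4. Reconcile the two documents: the Protocol's 12-month work analysis is missing from the SAP, and the SAP names 9 months as a primary endpoint beside 6 months whereas the Protocol names 6 months alone.

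The cost is wording, since the monthly Work Update Forms already supply the data. There are two downsides. The interval contrasts have less power, because they no longer include the early difference. They also measure whether more work continues, including jobs started earlier and kept, and do not isolate a new effect of the intervention; the text should say so.
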